**General AE Management and Dose Modification Guidelines**

There will be no dose reduction for atezolizumab in this study.

Patients may temporarily suspend study treatment for up to 84 days (12 weeks) beyond the scheduled date of delayed infusion if study drug-related toxicity requiring dose suspension is experienced. If atezolizumab is held because of AEs for 84 days beyond the scheduled date of infusion, the patient will be discontinued from atezolizumab and will be followed for safety and efficacy as specified in this protocol. If the AE resolves within 84 days and the patient is receiving corticosteroid therapy for the event, atezolizumab may be held for longer than 84 days (up to 4 weeks) in order to allow tapering of the steroid dose to  $\leq 10$  mg oral prednisone or equivalent.

Dose interruptions for reasons other than toxicity, such as surgical procedures, may be allowed. The acceptable length of interruption will be at the discretion of the study PI in consultation with CTEP.

The primary approach to grade 1 to 2 irAEs is supportive and symptomatic care with continued treatment with atezolizumab; for higher-grade irAEs, atezolizumab should be withheld and oral and/or parenteral steroids administered. Recurrent grade 2 irAEs may also mandate withholding atezolizumab or the use of steroids. Assessment of the benefit risk balance should be made by the investigator, with consideration of the totality of information as it pertains to the nature of the toxicity and the degree of clinical benefit a given patient may be experiencing prior to further administration of atezolizumab. Atezolizumab should be permanently discontinued in patients with life threatening irAEs.

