#### Pulmonary events

Dyspnea, cough, fatigue, hypoxia, pneumonitis, and pulmonary infiltrates have been associated with the administration of atezolizumab. Patients will be assessed for pulmonary signs and symptoms throughout the study and will have computed tomography (CT) scans of the chest performed at every tumor assessment.

All pulmonary events should be thoroughly evaluated for other commonly reported etiologies such as pneumonia or other infection, lymphangitic carcinomatosis, pulmonary embolism, heart failure, chronic obstructive pulmonary disease, or pulmonary hypertension. Management guidelines for pulmonary events are provided in the table below.

Event	Management
Pulmonary event, Grade 1	
 
Continue atezolizumab and monitor closely.
 
Re-evaluate on serial imaging.
 
Consider patient referral to pulmonary specialist.
 

Pulmonary event, Grade 2	
 
Withhold atezolizumab for up to 12 weeks after event onset.a
 
Refer patient to pulmonary and infectious disease specialists and consider bronchoscopy or BAL.
 
Initiate treatment with corticosteroids equivalent to 1–2 mg/kg/day oral prednisone.
 
If event resolves to Grade 1 or better, resume atezolizumab.b
 
If event does not resolve to Grade 1 or better while withholding atezolizumab, permanently discontinue atezolizumab.
 
For recurrent events, treat as a Grade 3 or 4 event.
 

Pulmonary event, Grade 3 or 4	
 
Permanently discontinue atezolizumab.
 
Bronchoscopy or BAL is recommended.
 
Initiate treatment with corticosteroids equivalent to 1–2 mg/kg/day oral prednisone.
 
If event does not improve within 48 hours after initiating corticosteroids, consider adding an immunosuppressive agent.
 
If event resolves to Grade 1 or better, taper corticosteroids over <math>\geq 1</math> month.
 

BAL bronchoscopic alveolar lavage

a Atezolizumab may be withheld for a longer period of time (*i.e.*, 12 weeks after event onset) to allow for corticosteroids (if initiated) to be reduced to the equivalent of  $\leq 10$  mg/day oral prednisone. The acceptable length of the extended period of time must be determined by the investigator and the Medical Monitor.

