Symptomatic hyperthyroidism	
 
Withhold atezolizumab.
 
Initiate treatment with anti-thyroid drug such as methimazole or carbimazole as needed.
 
Consider patient referral to endocrinologist.
 
Resume atezolizumab when symptoms are controlled and thyroid function is improving.
 
Permanently discontinue atezolizumab.
 

Symptomatic adrenal insufficiency, Grade 2–4	
 
Withhold atezolizumab for up to 12 weeks after event onset.a
 
Refer patient to endocrinologist.
 
Perform appropriate imaging.
 
Initiate treatment with corticosteroids equivalent to 1–2 mg/kg/day IV methylprednisolone and convert to 1–2 mg/kg/day oral prednisone or equivalent upon improvement.
 
If event resolves to Grade 1 or better and patient is stable on replacement therapy, resume atezolizumab.b
 
If event does not resolve to Grade 1 or better or patient is not stable on replacement therapy while withholding atezolizumab, permanently discontinue atezolizumab.
 

Hyperglycemia, Grade 1 or 2	
 
Continue atezolizumab.
 

Event	Management
	
 
Investigate for diabetes. If patient has Type 1 diabetes, treat as a Grade 3 event. If patient does not have Type 1 diabetes, treat as per institutional guidelines.
 
Monitor for glucose control.
 

Hyperglycemia, Grade 3 or 4	
 
Withhold atezolizumab.
 
Initiate treatment with insulin.
 
Monitor for glucose control.
 
Consider referral to endocrinologist, particularly if patient is deemed to have atezolizumab-induced diabetes; if so, obtain C-peptide level paired with glucose, autoantibody levels (e.g. GAD65, islet cell autoantibodies), and hemoglobin A1C level.
 
If patient is found to have diabetic ketoacidosis or hyperglycemic hyperosmolar syndrome, treat as per institutional guidelines with appropriate management and laboratory values (e.g. anion gap, ketones, blood pH, etc.) reported.
 
Resume atezolizumab when symptoms resolve and glucose levels are stable.
 

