### Immune-Mediated Meningoencephalitis

Immune-mediated meningoencephalitis is an identified risk associated with the administration of atezolizumab. Immune-mediated meningoencephalitis should be suspected in any patient presenting with signs or symptoms suggestive of meningitis or encephalitis, including, but not limited to, headache, neck pain, confusion, seizure, motor or sensory dysfunction, and altered or depressed level of consciousness. Encephalopathy from metabolic or electrolyte imbalances needs to be distinguished from potential meningoencephalitis resulting from infection (bacterial, viral, or fungal) or progression of malignancy, or secondary to a paraneoplastic process.

All patients being considered for meningoencephalitis should be urgently evaluated with a CT scan and/or MRI scan of the brain to evaluate for metastasis, inflammation, or edema. If deemed safe by the treating physician, a lumbar puncture should be performed, and a neurologist should be consulted.

Patients with signs and symptoms of meningoencephalitis, in the absence of an identified alternate etiology, should be treated according to the guidelines in the table below.

Event	Management
Immune-related meningoencephalitis, all grades	
 
• Permanently discontinue atezolizumab.
 
• Refer patient to neurologist.
 
• Initiate treatment with corticosteroids equivalent to 1–2 mg/kg/day IV methylprednisolone and convert to 1–2 mg/kg/day oral prednisone or equivalent upon improvement.
 
• If event does not improve within 48 hours after initiating corticosteroids, consider adding an immunosuppressive agent.
 
• If event resolves to Grade 1 or better, taper corticosteroids over ≥1 month.
 

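### For a first Grade 2 immune-related event, the general atezolizumab paragraph in Section 8.2.2 says continue, most event tables in the same section say withhold or stop, and nothing says which governs

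*Combined protocol and SAP*

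**What the plan says.** All of the text is in protocol Section 8.2.2.

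The subsection General AE Management and Dose Modification Guidelines sets a default by grade:

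- Grades 1 and 2: "The primary approach to grade 1 to 2 irAEs is supportive and symptomatic care with continued treatment with atezolizumab".
- Above Grade 2: "for higher-grade irAEs, atezolizumab should be withheld and oral and/or parenteral steroids administered".
- A qualifier for recurrence: "Recurrent grade 2 irAEs may also mandate withholding atezolizumab or the use of steroids".
- A further sentence asks the investigator to weigh benefit against risk, including the nature of the toxicity, before dosing again.
- For the most serious events: "Atezolizumab should be permanently discontinued in patients with life threatening irAEs".

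The event tables that follow give row-by-row instructions. The Grade 2 pulmonary row reads "Withhold atezolizumab for up to 12 weeks after event onset", and the same instruction appears in the Grade 2 rows of several other tables. Some rows go further. The row headed "Immune-related meningoencephalitis, all grades" directs permanent discontinuation. A few rows agree with the general default, for example the one headed "Hyperglycemia, Grade 1 or 2", which continues atezolizumab.

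**The concern.** The general paragraph and the tables answer the same question: does a patient with a first Grade 2 immune-related event get the next dose? For most organ systems they answer it differently.

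Two sites could therefore manage the same event in opposite ways, and each could cite the protocol. Arm 1 exposure and the count of atezolizumab discontinuations could then depend partly on which paragraph a site used.

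Other parts of the protocol also need one rule to refer to:

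- Section 1.3 of the German group-specific appendix makes meeting the Section 8.2 discontinuation criteria a reason for permanently ending study treatment.
- Section 5.1 of that appendix cites Section 8.2 as a risk mitigation.
- Section 6.1 of the protocol requires major and critical deviations to be reported.
- Section 13.6 of the protocol has treatment administration verified for all patients at selected sites.

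**Working it through.** There is no plan figure to reproduce and no power or alpha calculation. The check compares each table row covering Grade 2 with the general default for a first Grade 2 event, which is to continue.

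| Event row covering Grade 2 | Table instruction | Class |
|---|---|---|
| Pulmonary | withhold | withhold |
| Diarrhea or colitis | withhold | withhold |
| Symptomatic adrenal insufficiency (2–4) | withhold | withhold |
| Hypophysitis (2 or 3) | withhold | withhold |
| Ocular | withhold | withhold |
| Myocarditis (myocarditis table) | withhold | withhold |
| Pancreatitis (2 or 3) | withhold | withhold |
| Neuropathy, including facial paresis | withhold | withhold |
| Renal | withhold | withhold |
| Myocarditis (2–4, pericardial table) | stop permanently | stop |
| Pericardial disorders (2–4) | stop permanently | stop |
| Myelitis (printed under the myositis heading) | stop permanently | stop |
| Meningoencephalitis (all grades) | stop permanently | stop |
| Myasthenia gravis / Guillain-Barré (any grade) | stop permanently | stop |
| Stevens-Johnson / toxic epidermal necrolysis (any grade) | stop permanently once confirmed | stop |
| Hepatic | withhold if longer than 5 days | conditional |
| Amylase/lipase | continue at >1.5–2.0 × ULN; asymptomatic >2.0–5.0 × ULN handled as Grade 3, i.e. withhold | conditional |
| Dermatologic | continue | agrees |
| Hyperglycemia (1 or 2) | continue, except type 1 diabetes, handled as Grade 3 | agrees |
| Infusion reaction / cytokine release | interrupt the infusion, restart at half rate | separate type of rule |

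**Count.** 9 withhold + 6 stop + 2 conditional + 2 agree + 1 separate = 20 rows. Withhold or stop outright: 9 + 6 = 15, and 15/20 = 75%. With the conditional rows: 17/20 = 85%.

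**Narrower count.** Leave out the infusion-reaction and Stevens-Johnson rows and treat the shared myocarditis/pericardial cell as one row: 20 − 1 − 1 − 1 = 17 rows. Outright withhold or stop is then 9 + 4 = 13 of 17 (76%), or 14 of 17 (82%) with hepatic events over 5 days. Rows without a grade, such as thyroid disorders and suspected HLH/MAS, are in neither count.

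**Does the recurrence qualifier close the gap?** No. It makes recurrence the trigger at Grade 2, whereas the tables act on the first event. The pulmonary table treats recurrence as Grade 3 or 4, which means permanent discontinuation, while the general paragraph says only that withholding or steroids may be needed.

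**Grade 3.** The pulmonary, hepatic, ocular and renal tables stop permanently at Grade 3. The general paragraph says to withhold above Grade 2.

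**Tables against each other.** Grade 2 myocarditis is withheld, with resumption possible, in the myocarditis table. It is permanently discontinued in the table under pericardial disorders.

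**Is there a tie-breaker?** Three candidates were read:

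- Section 8.2 applies the greatest reduction when several adverse events occur together.
- Section 8.2.1 applies the most stringent reduction, for mFOLFOX6.
- The Management of Specific AEs subsection refers sites to the Investigator's Brochure for several event types.

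None ranks the event tables against the general paragraph.

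**The case against.** The best counter-argument is that the section moves from general to specific guidance. Several event subsections (myocarditis, pericardial disorders, meningoencephalitis, nephritis, myositis) tell the site to treat according to the table, and the others present their tables as the management guidelines for that event. The general paragraph describes a primary approach and leaves room for judgment. Many readers would simply follow the table.

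Much of that stands. It makes it less likely that sites would dose from the general paragraph, and the documents give no evidence that any did. But the protocol never states this order of precedence, and a default to continue does not become consistent with a row that says withhold or stop because judgment is allowed. Following the tables also leaves Grade 2 myocarditis unresolved, because there the tables disagree.

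Three stronger readings are tempting and are not supported:

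- **That the general paragraph withholds only above Grade 2.** It also allows withholding for recurrent Grade 2 events and asks for a benefit-risk assessment.
- **That the Grade 3 rows flatly contradict it.** The paragraph does not confine permanent discontinuation to life-threatening events, so these rows are stricter than the default. A patient who has stopped is also not being dosed.
- **That Grade 4 rows allowing resumption break the life-threatening rule.** The adrenal row for Grades 2–4 does say "If event resolves to Grade 1 or better and patient is stable on replacement therapy, resume atezolizumab", and the hyperglycemia and amylase/lipase rows also allow a return to dosing. But the general paragraph speaks of life-threatening events, not Grade 4. Reading the two as the same is an added assumption, weakest for laboratory elevations.

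One limit on the stop rows: a footnote in the neurologic table allows resumption to be considered after full recovery, so that permanent stop is not absolute.

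**Conclusion.** The point holds for first Grade 2 events. The general default is to continue, most rows covering Grade 2 withhold or stop, and no sentence says which applies. The share is 15 of 20 rows outright, or 13 of 17 on the narrower count, so the word most does not depend on how shared or conditional rows are scored. The Grade 2 myocarditis conflict is separate and holds on its own. The Grade 3 difference is real but weaker.

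This is a safety-relevant conflict between stated rules. The documents do not support a claim about the trial result. A row count is not a patient count, and no figure is given for affected patients, exposure or disease-free survival. Under Section 13.0, efficacy is analysed by intention to treat, so assignment to arm is unaffected. Any influence would run through the treatment delivered, the safety profile and the classification of deviations.

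The conclusion rests on the protocol text alone. The Investigator's Brochure was not available, and a precedence rule there would change the position, though the protocol would still need to cite it.

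**What to change.** Three wording changes in Section 8.2.2:

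1. Reconcile the general paragraph with the event tables for Grade 2, and make the relation at Grade 3 explicit.
2. Reconcile the two entries for Grade 2 myocarditis.
3. State which text governs when the general paragraph and a table differ.

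Which instruction is clinically right is for the sponsor and its medical experts to decide. This review proposes none.

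The cost is an edit to one paragraph and the myocarditis entries, plus a memo to sites. Sample size, analyses and data collection do not change. The German appendix planned last treatment there for February 2023. If Arm 1 dosing is over, which is an assumption, the clarification still helps in classifying past deviations and in interpreting Arm 1 exposure and discontinuations.

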#### Management of Specific AEs

Management of certain AEs of concern, including immune-related pneumonitis, hepatitis, colitis, endocrinopathies, pancreatitis, neuropathies, meningoencephalitis, and potential ocular toxicities are presented in the Atezolizumab Investigator's Brochure. See the Agent Administration Guidelines including the “**Administration of First and Subsequent Atezolizumab Infusions**” table for guidelines for the management of Infusion Related Reactions and Anaphylaxis.

Atezolizumab has been associated with risks such as the following: IRRs and immune-related hepatitis, pneumonitis, colitis, pancreatitis, diabetes mellitus, hypothyroidism, hyperthyroidism, adrenal insufficiency, hypophysitis, Guillain-Barré syndrome, myasthenic syndrome or myasthenia gravis, facial paresis, myelitis, meningoencephalitis, myocarditis, pericardial disorders, nephritis, myositis, and severe cutaneous adverse reactions. Immune-mediated reactions may involve any organ system and may lead to hemophagocytic lymphohistiocytosis and macrophage activation syndrome. Neutropenia and lymphopenia associated with chemotherapy may increase the risk for developing an infection in patients receiving atezolizumab in combination with chemotherapy.

#### Pulmonary events

Dyspnea, cough, fatigue, hypoxia, pneumonitis, and pulmonary infiltrates have been associated with the administration of atezolizumab. Patients will be assessed for pulmonary signs and symptoms throughout the study and will have computed tomography (CT) scans of the chest performed at every tumor assessment.

All pulmonary events should be thoroughly evaluated for other commonly reported etiologies such as pneumonia or other infection, lymphangitic carcinomatosis, pulmonary embolism, heart failure, chronic obstructive pulmonary disease, or pulmonary hypertension. Management guidelines for pulmonary events are provided in the table below.

Event	Management
Pulmonary event, Grade 1	
 
Continue atezolizumab and monitor closely.
 
Re-evaluate on serial imaging.
 
Consider patient referral to pulmonary specialist.
 

Pulmonary event, Grade 2	
 
Withhold atezolizumab for up to 12 weeks after event onset.a
 
Refer patient to pulmonary and infectious disease specialists and consider bronchoscopy or BAL.
 
Initiate treatment with corticosteroids equivalent to 1–2 mg/kg/day oral prednisone.
 
If event resolves to Grade 1 or better, resume atezolizumab.b
 
If event does not resolve to Grade 1 or better while withholding atezolizumab, permanently discontinue atezolizumab.
 
For recurrent events, treat as a Grade 3 or 4 event.
 

Pulmonary event, Grade 3 or 4	
 
Permanently discontinue atezolizumab.
 
Bronchoscopy or BAL is recommended.
 
Initiate treatment with corticosteroids equivalent to 1–2 mg/kg/day oral prednisone.
 
If event does not improve within 48 hours after initiating corticosteroids, consider adding an immunosuppressive agent.
 
If event resolves to Grade 1 or better, taper corticosteroids over <math>\geq 1</math> month.
 

BAL bronchoscopic alveolar lavage

a Atezolizumab may be withheld for a longer period of time (*i.e.*, 12 weeks after event onset) to allow for corticosteroids (if initiated) to be reduced to the equivalent of  $\leq 10$  mg/day oral prednisone. The acceptable length of the extended period of time must be determined by the investigator and the Medical Monitor.

b If corticosteroids have been initiated, they must be tapered over  $\geq 1$  month to the equivalent of  $\leq 10$  mg/day oral prednisone before atezolizumab can be resumed.

### Hepatic events

Immune-mediated hepatitis has been associated with the administration of atezolizumab. Eligible patients must have adequate liver function, as manifested by measurements of total bilirubin and hepatic transaminases, and liver function will be monitored throughout study treatment. Management guidelines for hepatic events are provided in the table below.

Patients with right upper-quadrant abdominal pain and/or unexplained nausea or vomiting should have liver function tests (LFTs) performed immediately and reviewed before administration of the next dose of study drug.

For patients with elevated LFTs, concurrent medication, viral hepatitis, and toxic or neoplastic etiologies should be considered and addressed, as appropriate.

Event	Management
Hepatic event, Grade 1	
 
Continue atezolizumab.
 
Monitor LFTs until values resolve to within normal limits or to baseline values.
 

Hepatic event, Grade 2	
All events:
 
 
Monitor LFTs more frequently until return to baseline values.
 
 
Events of >5 days' duration:
 
 
Withhold atezolizumab for up to 12 weeks after event onset.a
 
Initiate treatment with corticosteroids equivalent to 1–2 mg/kg/day oral prednisone.
 
If event resolves to Grade 1 or better, resume atezolizumab.b
 
If event does not resolve to Grade 1 or better while withholding atezolizumab, permanently discontinue atezolizumab.
 

Hepatic event, Grade 3 or 4	
 
Permanently discontinue atezolizumab.
 
Consider patient referral to gastrointestinal specialist for evaluation and liver biopsy to establish etiology of hepatic injury.
 
Initiate treatment with corticosteroids equivalent to 1–2 mg/kg/day oral prednisone.
 
If event does not improve within 48 hours after initiating corticosteroids, consider adding an immunosuppressive agent.
 
If event resolves to Grade 1 or better, taper corticosteroids over ≥1 month.
 

LFT = liver function test.

a Atezolizumab may be withheld for a longer period of time (*i.e.*, >12 weeks after event onset) to allow for corticosteroids (if initiated) to be reduced to the equivalent of ≤10 mg/day oral prednisone. The acceptable length of the extended period of time must be determined by the investigator.

b If corticosteroids have been initiated, they must be tapered over ≥1 month to the equivalent of ≤10 mg/day oral prednisone before atezolizumab can be resumed.

### Gastrointestinal events

Immune-mediated colitis has been associated with the administration of atezolizumab. Management guidelines for diarrhea or colitis are provided in the table below.

All events of diarrhea or colitis should be thoroughly evaluated for other more common etiologies. For events of significant duration or magnitude or associated with signs of systemic inflammation or acute-phase reactants (e.g., increased C-reactive protein, platelet count, or bandemia): Perform sigmoidoscopy (or colonoscopy, if appropriate) with colonic biopsy, with three to five specimens for standard paraffin block to check for inflammation and lymphocytic infiltrates to confirm colitis diagnosis.

Event	Management
Diarrhea or colitis, Grade 1	
 
Continue atezolizumab.
 
Initiate symptomatic treatment.
 
Endoscopy is recommended if symptoms persist for >7 days.
 
Monitor closely.
 

Event	Management
Diarrhea or colitis, Grade 2	
 
• Withhold atezolizumab for up to 12 weeks after event onset.a
 
• Initiate symptomatic treatment.
 
• Patient referral to GI specialist is recommended.
 
• For recurrent events or events that persist >5 days, initiate treatment with corticosteroids equivalent to 1–2 mg/kg/day oral prednisone.
 
• If event resolves to Grade 1 or better, resume atezolizumab.b
 
• If event does not resolve to Grade 1 or better while withholding atezolizumab, permanently discontinue atezolizumab.
 

Diarrhea or colitis, Grade 3	
 
• Withhold atezolizumab for up to 12 weeks after event onset.a
 
• Refer patient to GI specialist for evaluation and confirmatory biopsy.
 
• Initiate treatment with corticosteroids equivalent to 1–2 mg/kg/day IV methylprednisolone and convert to 1–2 mg/kg/day oral prednisone or equivalent upon improvement.
 
• If event resolves to Grade 1 or better, resume atezolizumab.b
 
• If event does not resolve to Grade 1 or better while withholding atezolizumab, permanently discontinue atezolizumab.
 

Diarrhea or colitis, Grade 4	
 
• Permanently discontinue atezolizumab.
 
• Refer patient to GI specialist for evaluation and confirmation biopsy.
 
• Initiate treatment with corticosteroids equivalent to 1–2 mg/kg/day IV methylprednisolone and convert to 1–2 mg/kg/day oral prednisone or equivalent upon improvement.
 
• If event does not improve within 48 hours after initiating corticosteroids, consider adding an immunosuppressive agent.
 
• If event resolves to Grade 1 or better, taper corticosteroids over ≥1 month.
 

GI = gastrointestinal.

a Atezolizumab may be withheld for a longer period of time (*i.e.*, >12 weeks after event onset) to allow for corticosteroids (if initiated) to be reduced to the equivalent of ≤10 mg/day oral prednisone. The acceptable length of the extended period of time must be determined by the investigator.

b If corticosteroids have been initiated, they must be tapered over ≥1 month to the equivalent of ≤10 mg/day oral prednisone before atezolizumab can be resumed.

